Sponsor	The Peter Doherty Institute for Infection and Immunity
Study Centre:	Alfred Hospital
Study Question:	To assess the feasibility, toxicity and effects of high dose disulfiram and vorinostat in HIV individuals on suppressive ART
Primary Objectives	
Primary efficacy objective: To determine the effect of 28 days of high dose disulfiram with intermittent administration of 3 days of vorinostat on plasma HIV RNA in HIV infected individuals on suppressive ART
 
Primary tolerability objective: To determine the tolerability of 28 days of high dose disulfiram with intermittent administration of 3 days of vorinostat in HIV infected individuals on suppressive ART

Secondary Objective	To determine the effect of 28 days of high dose disulfiram with intermittent administration of 3 days of vorinostat on the frequency of latently infected CD4+ T cells in HIV infected individuals on suppressive ART
Inclusion Criteria:	
 - Age 18-65 years with documented HIV-1 infection - Receiving combination ART with plasma HIV RNA <50 copies/mL for >3 years - CD4+ T cell count >350/μL at screening - Able to provide informed consent - WOCBP with a negative pregnancy test at screening (visit #1) 1 AND agrees to use one of the following methods of contraception to avoid pregnancy 
 o Complete abstinence from penile-vaginal intercourse from 2 weeks prior to administration of high dose disulfiram, throughout the study, and for at least 2 weeks after discontinuation of all study medications o Double barrier method (male condom/spermicide, male condom/diaphragm, diaphragm/spermicide) o Any intrauterine device (IUD) with published data showing that the expected failure rate is <1% per year o Male partner sterilization confirmed prior to the female subject's entry into the study, and this male is the sole partner for that subject o Approved hormonal contraception (Where other medications to be used in the study (e.g., efavirenz and darunavir) are known,

	
or are likely, to significantly interact with systemic contraceptives, resulting in decreased efficacy of the contraceptive, then alternative methods of non-hormonal contraception are recommended)
 
 ○ Any other method with published data showing that the expected failure rate is < 1% per year. 
 – Women of non-child-bearing potential defined as: 
 ○ > 12 months of spontaneous amenorrhea and ≥ 45 years of age, or ○ Documented medical history of one of the following: hysterectomy, bilateral oophorectomy or tubal ligation. – Willing to abstain from alcohol consumption from one day before to 14 days after completing study therapy

Exclusion Criteria:
	
 – Current alcohol use disorder or hazardous alcohol use (>7 drinks per week for women or > 14 drinks per week for men) as determined by clinical evaluation – Current use of metronidazole or any drug formulation that contains alcohol or that might contain alcohol, including the gelatin capsule and liquid formulations of ritonavir, ritonavir/lopinavir, amprenavir and fosamprenavir, and alcohol-containing preparations such as cough syrups, or tonics – Current use of tipranavir or Maraviroc – Current use of zidovudine, stavudine or didanosine (as disulfiram potentially has potent irreversible inhibitory effects on mitochondrial metabolism and hence could exacerbate the toxicity of these drugs) – Concurrent use of rivaroxaban (a CYP3A metabolized medication) as the cytochrome P450 inhibitory effects of disulfiram on rivaroxaban are unknown – Current use of warfarin – Individuals who intend to modify antiretroviral therapy during the study period for any reason – Significant myocardial disease (current myocarditis or reduced left ventricular ejection fraction below the lower limit of normal) or diagnosed coronary artery disease – Significant renal disease (eGFR <50mL/min) – History of psychosis, seizure disorder, abnormal electroencephalogram or brain damage with significant persisting neurological deficit – Prior malignancy active within the previous 3 years except for local curable cancers that have been apparently cured, such as basal or squamous cell skin cancer, superficial bladder cancer or carcinoma in situ of the prostate, cervix or breast – Known hypersensitivity to disulfiram or vorinostat or contraindications to treatment with these agents – Participation in another LRA study or receipt of vorinostat or disulfiram within the previous 12 months before starting the investigational treatment (visit #2) – Any significant acute medical illness requiring hospitalization within preceding 8 weeks

	
 - Hepatitis B or C co-infection as determined by detection of HBsAg or HCV RNA (Individuals with prior hepatitis infection that is now cleared are eligible for enrolment) - Receipt of immunomodulating agents (excluding immunization) or systemic chemotherapeutic agents within 28 days prior to study entry - Current or recent gastrointestinal disease or surgery that may impact the absorption of the investigational drug - Active substance use that in the opinion of the investigator will prevent adequate compliance with study procedures - Women who are currently pregnant or breastfeeding - WOCBP who are unwilling or unable to use an acceptable method of contraception to avoid pregnancy (as specified in the inclusion criteria) - Unable or unwilling to adhere to protocol procedures - The following laboratory values within 3 weeks before starting the investigational drug (lab tests may be repeated to obtain acceptable values before failure at screening is concluded) 
 o Hepatic transaminases (AST or ALT) ≥ 3 x upper limit of normal (ULN) o Serum total bilirubin ≥ 1.5 x ULN o eGFR < 50 mL/min o Haemoglobin < 10.0 g/dL o Platelet count $\leq 100 \times 10^9/L$ o Absolute neutrophil count $\leq 1.5 \times 10^9/L$ o Serum potassium, magnesium, phosphorus outside normal limits o Total calcium (corrected for serum albumin) or ionized calcium \leq lower normal limits
Number of Planned Participants:	15
Investigational product:	Disulfiram (2000mg) tablets daily for 28 days (days 1 – 28) Vorinostat (400mg) tablets once daily on days 8, 9, 10 and days 22, 23, 24
Statistical Methods:	
Sample size: The primary comparison for study is the level of plasma HIV RNA on day 11 during disulfiram/vorinostat treatment compared to baseline. Based on two previous studies of latency reversing agents (LRAs), where treatment with disulfiram 2000 mg or romidepsin led to increases in plasma HIV RNA, we assume a pre-study mean plasma HIV RNA of 1 copy/mL and a standard deviation of 11 copies/mL. Based on these numbers, the study will require 14 participants to detect an increase in plasma HIV RNA of 10 copies/mL with 80% power at a 0.05 significance level. Targeted enrolment is 15 participants to accommodate for loss to follow-up.
 
Analyses of primary and secondary endpoints

	
The primary comparisons will be made using paired t-test or signed-rank test as appropriate. By applying the same statistical methods, we will also analyse changes in CA-US HIV RNA following administration of high dose disulfiram and vorinostat. We will use repeated measurement analysis of variance statistics and/or generalized estimating equation statistics to analyse overall changes in primary and secondary endpoints during study intervention by including all data points during study therapy. P-values <0.05 will be considered significant.
 
Assessment of tolerability will include all participants who have received at least one dose of disulfiram. AEs and SAEs will be summarized according to severity assessment showing the number and percentage of participants experiencing at least one event, the number of events, and the causality assessment. No formal statistical comparisons will be made - AE rates are presented for descriptive purpose

--	---

1. GLOSSARY OF ABBREVIATIONS & TERMS

Abbreviation	Description
AE	A dverse e vent
ART	A ntiretroviral t herapy
CA-US HIV RNA	C ell A ssociated U nspliced HIV RNA
CD4+ T-cells	White blood cells that are an essential part of the human immune system
CTCL	C utaneous T - c ell l ymphoma
DMSO	D imethyl s ulfo x ide
DNA	d eoxyribo n ucleic a cid
ECG	E lectro c ardi g raphy
eCRF	e lectronic c ase r eport f orm
eGFR	e stimated g lomerular f iltration r ate
HBsAg	h epatitis B s urface a ntigen
HCV	H epatitis C v irus
HDAC	H istone D e a cetylase
HDACi	H istone D e a cetylase i nhibitor
HIV	H uman I mmunodeficiency v irus
HREC	H uman R esearch E thics C ommittee
LRA	L atency R eversing A gents
LTR	HIV L ong- t erminal R epeat, the promotor for HIV transcription
PBMC	P eripheral B lood M ononuclear C ell
PCR	P olymerase C hain R eaction
pK	Pharmacokinetics
qPCR	q uantitative P olymerase C hain R eaction
RNA	R ibo n ucleic a cid
SAE	S erious a dverse e vent
SOC	S tandard o f c are

Abbreviation	Description
SUSAR	S suspected U nexpected S erious A dverse R eaction
TGA	T herapeutics G oods A dministration (Australia)
TILDA	T at/rev I nduced L imiting D ilution A ssay.
WOCBP	W omen o f C hild B earing P otential

3. INTRODUCTION/BACKGROUND INFORMATION

3.1 LAY SUMMARY

Antiretroviral therapy (ART) dramatically reduces HIV replication leading to restoration of immune function and a near normal life expectancy, but treatment is lifelong and there is no cure. The major barrier to a cure is the persistence of long lived CD4+ T-cells that contain a “silenced” form of HIV, called HIV latency.

The purpose of this research is to investigate whether it may be possible to reduce the amount of dormant HIV infection in immune cells, by “turning on” or activating the virus and hence force it out of the latently infected memory T cells. This leads to production of HIV by the cell, which will either die or will be recognised and eliminated by the immune system. As very few T cells are latently infected with HIV, the death of these cells is not expected to affect the function of the immune system and further infection of new cells is expected to be prevented by ART

This study is looking at whether taking a short course of two drugs: high dose disulfiram for 28 continuous days with 2 intermittent 3 day courses of vorinostat (on days 8 – 10 and on days 22-24 of treatment) in addition to regular ART, will activate virus production from latency. The ultimate aim of this research is to identify a potent intervention to reverse latency that could then be combined with other interventions to achieve HIV remission.

Disulfiram, (Antabuse®), is a licensed medication for the treatment of alcohol addiction. Disulfiram inhibits aldehyde dehydrogenase and therefore interferes with the metabolism of alcohol. Alcohol is broken down in the body to a compound called acetaldehyde. This is then normally broken down further by an enzyme in the liver called aldehyde dehydrogenase.

Study Name: Combination Latency Reversing Therapy with Disulfiram plus Vorinostat in HIV Infected Individuals on antiretroviral therapy (ART): A Single Arm, Clinical Trial

Protocol ID: MDS-IIS-55750

Version & date: 4.0, Dated 17 June 2019

Disulfiram stops this enzyme from working, causing an accumulation of acetaldehyde in the blood stream which causes unpleasant symptoms such as flushing, headaches, nausea and vomiting which are enough to deter people from drinking alcohol. In the laboratory and in a recent clinical trial in HIV-infected individuals on ART, high dose disulfiram was shown to increase production of HIV from latently infected cells and therefore this drug may have a potential role in eliminating HIV that persists on ART.

Vorinostat is an anti-cancer (antineoplastic or cytotoxic) drug, known as a Histone Deacetylase (HDAC) Inhibitor. HDACs are enzymes normally present in cells that affects regulation of gene expression, which is the process by which a gene's information is converted into the structures and functions of a cell. By inhibiting HDAC, vorinostat causes cancer cells to die. Through this mechanism Vorinostat is effective in the treatment of different types of cancer. Vorinostat is approved by the Australian Therapeutic Goods Administration (TGA) for the treatment of subcutaneous T-cell lymphoma (a type of skin cancer). In the laboratory and in several clinical trials in HIV-infected individuals on ART, vorinostat was shown to increase production of HIV from latently infected cells and therefore this drug may have a potential role in eliminating HIV that persists on ART. Both disulfiram and vorinostat are not approved by the TGA for the treatment of HIV.

This study involves study participants to attend the clinic at the Alfred hospital approximately 9 times over a 6 month period to attend specific study visits. These visits will take place at screening, baseline (day 0), days 8, 11, 22, 25, 28, 56 and 196 (month 6).

Study participants will be enrolled after all the inclusion criteria are met. During the course of the study, the investigators will meet regularly to monitor study progress and participant safety by reviewing all information, including side effects.

3.2 INTRODUCTION

One strategy aimed at reducing the frequency of latently infected cells in HIV-infected individuals on antiretroviral therapy (ART) is the use of pharmacological agents to reverse HIV latency, thereby initiating virus-mediated cell lysis or immune-mediated killing¹. Recent clinical trials of latency reversing agents (LRAs) in HIV infected subjects on ART, including histone deacetylase inhibitors (HDACi)²⁻⁴ and the anti-alcoholism drug disulfiram^{5,6}, have shown that inducing an increase in CA-US or plasma HIV RNA is possible. Yet, these interventions did not have a demonstrable effect on the frequency of latently infected cells or time to viral rebound after cessation of ART³, potentially because latency reversal alone didn't trigger an adequate immune response or cell death or that the potency of latency reversal with a single-agent intervention over a very short period of time, lacked sufficient potency, as suggested by recent in vitro studies⁷. It is highly likely that long term remission off ART will require interventions that lead to both a reduction in latently infected cells and an increase in HIV-specific immunity, therefore identifying a strategy to increase viral antigens on the surface of latently infected cells will be a key component of this strategy. Here we propose a single-arm clinical trial of high-dose disulfiram together with intermittent administration of the HDACi vorinostat in HIV-infected individuals on ART as a strategy to increase potency of latency reversal with low risk of increased toxicity

3.3 BACKGROUND INFORMATION

There are multiple factors that lead to the establishment and maintenance of HIV latency⁸. These include the low availability of key transcription factors in resting CD4+ T cells⁹ as well as the chromatin environment of the integrated provirus leading to transcriptional silencing or interference⁸. HDACi increase histone acetylation, which promotes initiation of HIV transcription, but additional blocks in RNA splicing, RNA export and low availability of cellular transcription factors may limit the efficiency of virus production¹⁰. It is plausible that targeting several latency mechanisms will enhance the expression of viral proteins or production of free virions in latently infected resting CD4+ T cells.

When resting CD4+ T cells from HIV-infected individuals on suppressive ART were exposed to combinations of LRAs ex vivo, there was a synergistic increase in HIV production, in some cases approaching that of maximal T cell activation¹¹. The most striking synergy was seen with combinations of potent HDACis such as romedepsin and the protein kinase C (PKC) agonist bryostatin-1, but their associated toxicities may not allow for clinical co-administration. Other combinations that are more feasible in the clinical setting, also showed at least additive effects in vitro. For example, in contrast to either drug alone, the combination of HDACi and disulfiram consistently increased levels of intracellular HIV RNA relative to DMSO (dimethyl sulfoxide) controls ex vivo¹¹. Synergy analyses indicated that HDACi and disulfiram reverse HIV latency by independent mechanisms¹¹. Whereas HDACi reverse HIV latency by promoting histone acetylation and chromatin relaxation¹², disulfiram activates HIV transcription by depletion of phosphatase and tensin homolog (PTEN), which alleviates inhibition of the Akt signalling pathway. Activated Akt phosphorylates hexamethylene bis-acetamide inducible 1 (HEXIM1), which subsequently causes release of positive transcription elongation factor b (p-TEFb) to enhance HIV transcription. P-TEFb is otherwise only present at very low levels in resting CD4+ T cells¹³.

Safety and efficacy of disulfiram and vorinostat as LRAs in vivo

Disulfiram and vorinostat have both been shown to increase HIV transcription in vitro¹⁴⁻¹⁶ and in clinical trials^{2,6,17}. With its long-standing use to treat alcoholism, favourable tolerability and lack of mutagenic potential, disulfiram can be administered for extended periods. Vorinostat (Zolinza®), is a pan HDAC inhibitor¹⁸ with regulatory approval for the treatment of cutaneous T cell lymphoma. Although less potent than the more recently licensed HDACi panobinostat and romidepsin, vorinostat has the advantage of being orally administered and has an extensive safety profile. In vitro, compared to other HDACi, vorinostat had minimal effects on suppressing HIV-specific T-cell function, in contrast to romidepsin which potently suppressed T-cell function¹⁹. Finally, we previously showed that vorinostat has acceptable tolerability during daily dosing for 14 days, which led to increases in HIV transcription in ART-suppressed HIV patients in blood and in rectal tissue and no adverse effects on HIV-specific T-cells in vivo². In addition, long term follow up of these participants for two years demonstrated no adverse clinical or virological effects of vorinostat in HIV-infected individuals on ART [Mota, submitted].

Here we propose to administer disulfiram at 2g/day for 28 days with two additional short courses of vorinostat. The rationale here is to give an LRA for a prolonged period alone and in combination. Disulfiram is the only LRA that has an appropriate toxicity profile, which would allow for prolonged administration. Based on our experience with two clinical studies of disulfiram in HIV infection given at standard dose (500mg/day) for 14 days⁵ and at high dose

(1 and 2 g/day) for 3 days⁶, we believe that administration at 2g/day for 28 days is safe and feasible. Previously, disulfiram was used in the clinical setting at relatively high doses ranging from 1-3 g²⁰ and up to 6g²¹ in individuals with alcoholism, and was generally reported to be safe with the most significant safety concern being fatal disulfiram-induced hepatitis, which is estimated to occur extremely rarely at 1 per 25,000 patients treated/year²⁰.

In addition, vorinostat will be administered on two occasions for 3 days each. In our study of 14 days of vorinostat, we observed maximal increase in both histone acetylation and US RNA after 8-24 hours of the initial dose and minimal adverse events². With repeated vorinostat dosing, we saw no evidence of a refractory response to vorinostat but a sustained increase in US RNA up to 84 days following repeated administration², however, others have reported a potential suppression of the effects of vorinostat after at least 4 courses of 3 days of vorinostat²². By administering vorinostat as two separate courses in this study, we will reduce the possibility of a refractory response. Furthermore, in this study we can assess whether addition of vorinostat after 7 days of disulfiram will lead to higher increases in plasma HIV RNA relative to disulfiram alone (first seven days of study) or if potential “priming” is occurring leading to an enhanced response after a second administration of 3 days of vorinostat.

It remains unclear whether the sequence of these two LRAs will have an impact on the potency of latency reversal. Most in vitro studies that have assessed combination latency reversal have administered the two agents concurrently^{11,29,30,31}. In this study, we believe the initial administration of disulfiram for 7 days prior to administration of vorinostat will provide additional information of the effects of high dose disulfiram that was not addressed in previous studies⁶.

In conclusion, combinations of LRAs that target different pathways that maintain HIV latency may significantly enhance the potency of latency reversal. As disulfiram and vorinostat have already been evaluated alone in HIV-infected individuals on ART, have additive effects on HIV transcription in vitro and ex vivo and have acceptable safety profiles, the combination of these two drugs is ideally suited for the first combination LRA study to be performed in HIV-infected individuals on ART.

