4.3 OUTCOME MEASURES

4.3.1 Primary endpoint

- Plasma HIV RNA on day 11 relative to baseline

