4.3.2 Secondary endpoints

- Tolerability as measured by the incidence and severity of adverse events
- Plasma HIV RNA relative to baseline at additional time points
- HIV transcription measured by cell-associated unspliced HIV RNA (CA-US HIV RNA) in peripheral blood CD4+ T cells relative to baseline
- Cell-associated total and integrated HIV DNA in peripheral blood CD4+ T cells relative to baseline
- The frequency of inducible virus as measured by Tat/rev limiting dilution assay (TILDA) in peripheral blood CD4+ T cells relative to baseline
- Concentrations of vorinostat and disulfiram (including its metabolites) in plasma
- p24 expression in CD4+ T-cells relative to baseline

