11.2 ANALYSES OF PRIMARY AND SECONDARY ENDPOINTS

The primary comparisons will be made using paired t-test or signed-rank test as appropriate. By applying the same statistical methods, we will also analyse whether changes in CA-US HIV RNA and plasma HIV RNA differ following administration of high dose disulfiram and vorinostat. We will use repeated measurement analysis of variance statistics and/or generalized estimating equation statistics to analyse overall changes in primary and secondary endpoints during study intervention by including all data points during study therapy. P-values <0.05 will be considered significant.

The tolerability population will include all participants who have received at least one dose of vorinostat or disulfiram. Adverse events (AEs) and serious adverse events (SAEs) will be summarized according to severity assessment showing the number and percentage of participants experiencing at least one event, the number of events, and the causality assessment. No formal statistical comparisons will be made – AE rates are presented for descriptive purposes.

11.3 GENE EXPRESSION DATA AND ADDITIONAL ANALYSES TO INVESTIGATE NEUROTOXICITY (SECTIONS 9.8 – 9.12)

RNA sequencing data will undergo standard bioinformatic analyses, which is performed by Australian Genome Research Facility (AGRF), Melbourne. This will include quality and adapter trimming, alignment, quantification and normalisation. RNA expression data will be mapped to a reference genome and gene expression levels will be compared across different time points to identify differentially expressed genes. Differential expression of gene pathways will be analysed using Kyoto Encyclopedia of Genes and Genomes (KEGG) and Reactome platforms.

Other additional analyses related to observed neurotoxicity include plasma levels of cytokines, biomarkers of neuronal injury, levels of histone acetylation, pTEFB and NFkB activation and effects of disulfiram with or without vorinostat on primary astrocytes, astrocyte cell lines and PBMCs. These data will be summarised using descriptive statistics. Where feasible different time points or conditions will be compared using paired t-test or signed-rank test.

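### Does the plan need to name the days for the vorinostat increment and for priming, which section 3.3 says the trial can assess?

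*Combined protocol and SAP*

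**What the plan says.** Section 3.3 (background) gives two things the design allows the investigators to look at. The first is "whether addition of vorinostat after 7 days of disulfiram will lead to higher increases in plasma HIV RNA relative to disulfiram alone", with disulfiram alone identified as the first seven days. The second is whether priming occurs, "leading to an enhanced response after a second administration of 3 days of vorinostat".

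The endpoints are defined differently. The primary endpoint in 4.3.1 is "Plasma HIV RNA on day 11 relative to baseline". Section 4.3.2 adds "Plasma HIV RNA relative to baseline at additional time points" and "HIV transcription measured by cell-associated unspliced HIV RNA (CA-US HIV RNA) in peripheral blood CD4+ T cells relative to baseline". All three use baseline as the reference.

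Section 11.2 uses a paired t-test or signed-rank test for the primary comparison. With the same methods it will examine "whether changes in CA-US HIV RNA and plasma HIV RNA differ following administration of high dose disulfiram and vorinostat". It then applies repeated-measures ANOVA and/or GEE to "overall changes in primary and secondary endpoints during study intervention by including all data points during study therapy". The Statistical Methods entry of the synopsis words the middle sentence more narrowly: "we will also analyse changes in CA-US HIV RNA following administration of high dose disulfiram and vorinostat".

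**The concern.** The protocol appears to promise an answer that its analysis section does not set out. By day 11 a participant has taken ten days of disulfiram as well as three of vorinostat. A rise from baseline therefore cannot show that vorinostat added anything, and no baseline-referenced contrast estimates that addition directly.

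The nearest sentence in 11.2 does not say what is being compared. It could mean before against after treatment, one RNA marker against the other, or disulfiram alone against the combination. The synopsis version speaks neither of a difference nor of plasma HIV RNA, the variable that 3.3 asks about. By contrast, section 9.8 does name a day 0 to 8 window and a day 8 to 11 window, but only for RNA sequencing.

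If the days were truly open, the contrast could be chosen after the results were seen. For priming, two reasonable choices could give different answers.

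**Working it through.** **The plan's own calculation.** Section 11.1 assumes an SD of 11 copies/mL for the increase, an increase of 10 copies/mL to detect, 80% power and a 0.05 level, and states 14 participants. An exact paired t-test (noncentral t, two-sided) gives n = 12, with power 81.7%. The stated 14 is matched by a signed-rank allowance, 12/0.864 = 13.9, or by a rise from 1 to 10 copies/mL (a difference of 9), for which the t-test needs 14. At n = 14, power for 10 copies/mL is 88.1%. This covers day 11 against baseline only; the documents give no calculation for the increment or for priming.

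**What the sampling fixes.** Single-copy plasma RNA is scheduled at every visit (Table 1). Days 8 and 22 are drawn before dosing (8.4, 8.6); days 11 and 25 are drawn 24 hours after the last dose of each course (8.5, 8.7). Write dX for the value on day X and B for baseline.

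- Increment: the combination's change less disulfiram's change is (d11 − B) − (d8 − B) = d11 − d8. Baseline cancels, so the two baseline-referenced changes already contain it.
- Priming, reading 1: second response against first, both from baseline, is (d25 − B) − (d11 − B) = d25 − d11.
- Priming, reading 2: second step against first step is (d25 − d22) − (d11 − d8).
- Reading 1 minus reading 2: (d25 − d11) − (d25 − d22) + (d11 − d8) = d22 − d8.

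The two readings agree when day 22 has the same level as day 8. They part after 14 more days of disulfiram, or with carry-over from the first course, if either moves day 22.

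**Precision.** The documents give no SD for these contrasts. Assume that every visit's change from baseline has SD 11 and that any two visits' changes correlate at r.

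- SD(d11 − d8), and equally SD(d25 − d11) = 11·√(2(1 − r)).
- SD of the double difference (reading 2) = 22·√(1 − r).
- 95% half-width at n = 14 = t(0.975, 13)·SD/√14 = 0.577·SD.
- Difference with 80% power at n = 14 = 0.810·SD.

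| r | SD, d11 − d8 | Half-width | 80% power at | SD, double difference | Half-width |
|---|---|---|---|---|---|
| 0 | 15.56 | 8.98 | 12.6 | 22.0 | 12.7 |
| 0.5 | 11.0 | 6.35 | 8.91 | 15.56 | 8.98 |
| 0.8 | 6.96 | 4.02 | 5.64 | 9.84 | 5.68 |
| 0.9 | 4.92 | 2.84 | 3.99 | 6.96 | 4.02 |

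All SDs, half-widths and detectable differences are in copies/mL. They are the same whether or not the plan names the days, so they describe how much the trial can learn about these questions and not any harm from the omission. With an assumed mean of 1 and an SD of 11 the changes may well be skewed, so the t-based widths are approximate.

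**The case for a change.** The strongest case for a change is that 3.3 states a capability that is part of the design rationale, that the samples for it are all scheduled, and that a few lines in 11.2 and the synopsis would close the gap. Version 4.0 also speaks of neurotoxicity as already observed (11.3), so one may ask whether virological results were known when the analyses were settled.

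Part of this stands. Section 11.2 names no days, the synopsis and 11.2 differ in wording, and a positive primary result must not be read as evidence that vorinostat added to disulfiram.

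The rest carries less weight. The increment has one natural definition, and the phase windows in 9.8 show that the authors think of the phases in the same way. The GEE or repeated-measures model uses all on-therapy points and can supply either contrast. The neurotoxicity remark concerns safety and says nothing about whether single-copy assay results had been seen.

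Naming the days would not remove the real limits. Day 11 minus day 8 also contains three further days of disulfiram with no concurrent control, and day 22 may carry over from the first course. Making the increment a secondary contrast would give formal standing, without a matching objective, to an estimate of low precision.

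**Conclusion.** No change is called for. This is missing detail on two exploratory questions, and an analyst can fill it sensibly from the schedule. No hypothesis, objective or endpoint in section 4 lacks an analysis, the day 11 against baseline comparison is valid for the effect of the whole regimen, and nothing in the plan as written produces a wrong result.

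The increment is day 11 minus day 8. This rests on reading 3.3 together with the pre-dose day 8 sample, which leaves little room for another choice. Priming is the only open item: its two readings differ by day 22 minus day 8, and showing both costs nothing in samples or visits. At n = 14, with SD 11 at each visit and r from 0.5 to 0.9, the 95% half-widths are 6.4 to 2.8 copies/mL for the increment and for day 25 minus day 11, and 9.0 to 4.0 for the double difference; all are wider if r is lower. These are estimates to describe with their intervals and are not a basis for firm claims. The different wording in the synopsis is a minor slip with no effect on the primary analysis.
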